3.1.2. Analysis of secondary outcomes

Analytical procedures for the secondary outcomes will follow those for the primary outcome. Each outcome will have its own appropriate confounders. As with the primary outcome, these confounders will be based on previous research and specified a priori. As needed, they will be supplemented by empirical analysis of the 20% subset, including baseline covariates specified in Appendix B, with a 10% change-in-estimate threshold for inclusion.

These confounders from the literature are available:

1. Preterm birth defined as delivery before 37 gestational weeks.
 - a. Same confounders as the primary outcome
2. Clinical diagnoses of depression.
 - a. History of anxiety and depression (9)
 - b. Smoking (9)
 - c. Past pregnancy complications or loss (9)

Unavailable: Lack of partner or social support or having a problematic relationship, a history of abuse or child abuse, having had an unplanned or unwanted pregnancy, perceived stress, cognitive style (including “pessimism, anger and rumination; a tendency to be nervous, worried or shy; low self-esteem and low self-efficacy; and high levels of neuroticism or psychoticism”), and single marital status (9).
3. Anxiety rates (using ICD10 codes).
 - a. History of anxiety and depression (9)
 - b. Smoking (9)
 - c. Past pregnancy complications or loss (9)

Unavailable: Same as anxiety (9).
4. Referral to behavioral health
 - a. No confounders identified
5. Referral to social work
 - a. No confounders identified
6. Preeclampsia
 - a. Prior pre-eclampsia (10)
 - b. Chronic hypertension (10)
 - c. Pre-gestational diabetes (10)
 - d. BMI >30 (10)

Unavailable: Antiphospholipid antibody syndrome (10).
7. Sufficient gestational weight gain
 - a. Pre-pregnancy BMI (11)
 - b. Age (11)

Unavailable: Family violence; marital status; food insecurity; maternal pregravid metabolic status; hyperemesis gravidarum; anorexia; past bariatric surgery (11).
8. Number of prenatal appointments attended
 - a. No confounders identified
9. Percent of required prenatal appointments attended
 - a. No confounders identified

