1.6. Overview of proposed analyses

EG will analyze the primary, secondary, and exploratory outcomes for the trial data. LH will generate data and run models as needed so that EG remains blinded to the identity of each cohort (see section 2.5).

The primary analyses will be multiple linear regression models estimating average treatment effects of the MHP app. Secondarily, dose-response models will be created for the primary and secondary outcomes in order to understand the moderating effects of app usage.

The primary and secondary outcomes for the study will come from electronic health record (EHR) data for trial participants. Given the source and the nature of care for women who deliver in the UPMC system, few outcome data are missing data. As such, imputation will not be used to account for missing outcome data. Instead, participants will be excluded from analyses, if their outcome data is missing for an outcome measure.

As a sensitivity analysis, propensity score matching will be used to create similar cohorts of participants, excluding participants whose propensity scores are outside the overlap in the covariate distributions for the covariates that predict downloading the MHP app (see section 3.1.5). We will calculate average treatment effects for these matched subsets of participants. Inverse probability of treatment weighting will be used as an additional sensitivity analysis to account for the potential lack of overlap in covariate distributions between the study cohorts.

2. Data analysis plan – data description

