3.1.1. Analysis of primary outcomes

The difference in gestational weeks at birth will be evaluated using a linear effects model accounting for confounders of preterm birth, as measured at baseline. We estimate that about 57 out of 12,344 deliveries are for a second pregnancy for participants included in the sample given that 0.464% of participants who downloaded the app had two deliveries in the sample. We have included these women in the sample because we cannot exclude similar women in the usual care cohort given limitations in our data. Likewise, we cannot account for random effects of multiple deliveries using a mixed effects model.

Baseline study variables will be included as confounders in the model if (a) the literature has identified the variable as a confounder of preterm birth risk and (b) they might plausibly have influenced participants' decision to download the app. If, for a variable, the evidence on condition (a) is inconclusive and condition (b) is possible, we will examine the data and include the variable if it passes a 10% change-in-estimates threshold for the outcome or for the likelihood of downloading the app. The change-in-estimate will be calculated by adding each study variable to the model from the literature individually. Only baseline variables will be evaluated as potential confounders, as they could not have been affected by use of the app.

We will report the results of two models for each outcome, one using only confounders identified in the literature and one adding confounders identified empirically (Appendix A). Including fewer confounders will reduce the likelihood that the average treatment effect applies only to an unrepresentative subset of the population. Including additional confounders will reduce the likelihood of statistical bias in estimating the average treatment effect.

The dataset contains many known confounders of preterm birth that could be included in the model including:

- Previous preterm birth (3)
- Race (3)
- Low body-mass index (3,4)
- Insurance type (5)
- Area deprivation index (6)
- Multiple gestations (3)
- Previous spontaneous abortions (7)
- Hypertension (3)
- Diabetes (3)
- Tobacco use (3)

There are also many known predictors of preterm birth that are not in the EHRs, hence not available for this study. They include educational attainment, marital status, interpregnancy interval, relatives who delivered preterm, and genetic predictors of preterm birth (3).

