Some collected covariates are specific to this dataset. One is hospital location, which may capture differences in resources, practices, and patient populations. The second is the date of the first visit recorded in Epic, which may capture factors like access to care or social conditions (e.g., the pandemic). We will include hospital location as a variable in all models. We will not include date of first visit as it might be correlated with ones that affect the effectiveness of the app over time.

Residual plots will be used to evaluate the models for heteroskedasticity and the need for using robust standard errors, in order to allow for violations in the assumption that observations are independent and identically distributed (8).

Differences between the cohorts will be described using adjusted mean differences and p-values. Results will be considered significant at $p < 0.05$.

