3.1.4. Dose-response analysis

A dose-response analysis will be used to test usage as a mediator of each outcome. Multiple measurements of usage were collected and are listed in Appendix A. Metrics specified in section 2.3 will be created by assessing whether the participant used any app activity on a given day. Logging into the app without activity will not count as app usage because this information was not collected for the full study period. Activity use is also more likely to be associated with engagement with the app than is login alone. Daily usage and weekly usage will be the dependent variables for the dose-response models. As an exploratory analysis, the PCI may be analyzed as a dependent variable. The dose-response relationship will be analyzed for the primary and secondary outcomes using a multiple linear effects model and the confounder adjustment method (12). The model for adherence will be created using 20% of the unblinded data. The dose-response effects for the primary outcome will be reported in the manuscript. The dose-response effect for the secondary outcomes will be reported in the supplemental material.

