EST_GEST_AGE_DAYS	gestational age at the time of birth	Primary outcome
MOM_DELIVERY_WT	weight of mother at time of delivery (kg)	Secondary outcome
PREGANY_DEPRESSION	Diagnosis of depression or active depression at some point during pregnancy (would also be 1 if PREGSTART_DEPRESSION is 1) (binary variable)	Secondary outcome
PREGANY_ANXIETY	Diagnosis of anxiety or active anxiety at some point during pregnancy (would also be 1 if PREGSTART_ANXIETY is 1) (binary variable)	Secondary outcome
PREGANY_PREE	Preeclampsia diagnosed or listed as active problem at any visit while pregnant (binary variable)	Secondary outcome
PNV_COUNT	Number of prenatal appointments attended	Secondary outcome
PNV_TOTSCHED	Number of prenatal appointments scheduled (blank if the same as PNV_COUNT i.e. they didn't cancel any appointments)	Secondary outcome
PREGANY_BEHAVIORALREF	Behavioral health referral at some point during pregnancy (binary variable)	Secondary outcome
PREGANY_SWREF	Social work referral at some point during pregnancy (binary variable)	Secondary outcome
BABY_DISPOSITION	baby's disposition after birth (home health agency, home/self care, children's hospital, cease to breathe, etc)	Exploratory outcome
STILLBORN	whether this baby was stillborn (binary variable)	Exploratory outcome
C_SECTION	Had c-section (binary variable)	Exploratory outcome
BIRTH_WEIGHT	baby's birth weight in grams	Exploratory outcome
NICU_DELIVERYADMISSION	whether the baby was brought to the NICU (binary variable)	Exploratory outcome
ASSUMED_INDUCTION	If a delivery was by c-section prior to 259 days gestation, but there is no documentation of induction then we assume	Exploratory outcome

	it was indicated and this column has a 1 (binary variable). Otherwise, it's 0. Definition came from Hy.	
INDICATED_ONSET	When a delivery form documents that a delivery was induced but not for PROM (binary variable). Definition came from Hy.	Exploratory outcome
CURRENT_PPROM	premature rupture of membranes; diagnosis of O42* during current delivery (binary variable).	Exploratory outcome
VISITNUMBER_F2F	Number of face-to-face visits when pregnant.	Exploratory outcome
PREGANY_PREGINDUCEDHTN_NOPROT	Gestational hypertension without significant proteinuria, could occur during any trimester, childbirth, or puerperium; Diagnosed or listed as active problem at any visit while pregnant. Definition came from EPIC codes	Exploratory outcome

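### The yes/no secondary outcomes go through a linear model whose robust standard errors depend on residual plots; robust errors should be the default (minor)

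*SAP*

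**What the plan says.** SAP section 3.1.2, on the nine secondary outcomes: "Analytical procedures for the secondary outcomes will follow those for the primary outcome". The primary procedure is set out in section 3.1.1: "The difference in gestational weeks at birth will be evaluated using a linear effects model accounting for confounders of preterm birth, as measured at baseline". Results are to be given as follows: "Differences between the cohorts will be described using adjusted mean differences and p-values". Standard errors are covered by one sentence in the same section: "Residual plots will be used to evaluate the models for heteroskedasticity and the need for using robust standard errors". It gives no criterion for reading the plots and no default.

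Two other sections point to the same model family. Section 1.6: "The primary analyses will be multiple linear regression models estimating average treatment effects of the MHP app". Section 3.1.4 names a multiple linear effects model for the dose-response analysis of the primary and secondary outcomes. Logistic regression appears only in section 3.1.5, for the propensity score. No logistic, Poisson or other model is named for any outcome.

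By type, the secondary outcomes in section 1.1.2 and Appendix A are:
- **Yes/no (six):** preterm birth, depression, anxiety, behavioral health referral, social work referral and preeclampsia.
- **Probably yes/no (one):** sufficient gestational weight gain, if coded as meeting the guideline. Appendix A supplies delivery weight in kg, so the coding is not fixed there.
- **Count (one):** prenatal appointments attended.
- **Proportion (one):** required appointments attended.

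**The concern.** For a 0/1 outcome with risk p the variance is p(1-p). Any predictor of risk therefore also changes the variance, and the single residual variance assumed by ordinary least squares is wrong unless all risks have the same p(1-p). This is known before any data are seen. Residuals from such a model fall on two bands, so a plot adds nothing to the decision.

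The SAP's depression model shows this without any assumed rate. Appendix A sets the depression outcome to 1 whenever depression was present at the first prenatal visit, and section 3.1.2 lists history of anxiety and depression as a covariate. If that history is entered as the baseline depression indicator, the outcome variance in that subgroup is exactly zero. The anxiety model has the same structure.

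At stake are the confidence intervals and p-values of the secondary outcomes. They can be slightly too narrow or too wide, and which set is reported rests on a visual judgement made after outcome data are available.

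**Working it through.** **1. The plan's own figure.** Section 1.5 gives 7147 and 5197 deliveries, SD 10 days, 80% power and a 0.51 day difference. The detectable difference is SD × (z0.975 + z0.80) × √(1/7147 + 1/5197) = 10 × 2.8016 × 0.018230 = 0.511 day. The figure reproduces (two-sided 5% level), so the cohort sizes are usable. It concerns the primary outcome only; the SAP gives no power or event rates for the secondary outcomes.

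**2. Unadjusted comparison of a 0/1 outcome.** With va = pa(1-pa) and vb = pb(1-pb):
- constant-variance SE = √[ v × (1/na + 1/nb) ], where v = (na·va + nb·vb)/(na + nb);
- robust SE = √( va/na + vb/nb ).

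Worked case, 3% (n = 7147) against 5% (n = 5197): va = 0.0291, vb = 0.0475, v = 0.036847. Constant-variance SE = √(0.036847 × 0.00033234) = 0.003499. Robust SE = √(0.0291/7147 + 0.0475/5197) = 0.003635. Ratio 0.963. Actual coverage of a nominal 95% interval = 2Φ(1.96 × ratio) - 1 = 94.1%.

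All rates below are assumptions. Both allocations are shown because section 1.5 keeps the identity of the larger cohort blinded.

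| Assumed rates | Lower rate in the larger cohort: ratio (coverage) | Lower rate in the smaller cohort: ratio (coverage) |
|---|---|---|
| 10% v 10% | 1.000 (95.0%) | 1.000 (95.0%) |
| 8% v 10% | 0.984 (94.6%) | 1.016 (95.4%) |
| 5% v 8% | 0.967 (94.2%) | 1.035 (95.7%) |
| 3% v 5% | 0.963 (94.1%) | 1.039 (95.8%) |
| 10% v 20% | 0.957 (93.9%) | 1.045 (96.0%) |
| 5% v 10% | 0.952 (93.8%) | 1.050 (96.0%) |
| 2% v 4% | 0.950 (93.7%) | 1.053 (96.1%) |

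**3. Adjusted model with no app effect: depression.** Assume 20% have baseline depression (outcome fixed at 1, variance 0), 8% of the others are newly diagnosed (variance 0.08 × 0.92 = 0.0736), and download rates are 55% without and 80% with baseline depression.
- Residual variance: 0.8 × 0.0736 = 0.05888.
- Within-stratum variance of download: D = 0.8 × 0.55 × 0.45 + 0.2 × 0.80 × 0.20 = 0.198 + 0.032 = 0.230.
- n × constant-variance sampling variance: 0.05888/0.230 = 0.2560.
- n × robust sampling variance: 0.198 × 0.0736/0.230² = 0.2755.
- Ratio of standard errors: √(0.2560/0.2755) = 0.964; coverage 94.1%.

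With 70% in place of 80%, D = 0.240 and the ratio is 0.985. With equal download rates it is 1.000.

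**4. Simulation.** Data sets of 12,344 with one binary covariate were simulated 1000 times per scenario, for binary and overdispersed count outcomes under assumed settings. The mean ratio of ordinary to robust standard error ran from 0.988 to 1.031. The two count scenarios gave 1.004 and 1.005.

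**The case against.** **The linear model might not carry over.** One could read section 3.1.2 as passing on only the method of choosing confounders. Sections 1, 1.6 and 3.1.4 all describe linear models, and no other outcome model is named, so this reading does not stand. If it did, the yes/no outcomes would have no model at all.

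**The plan already anticipates the problem.** Section 3.1.1 raises heteroskedasticity, names robust errors and cites a source. The two-band pattern may well lead the reader of the plots to use them. The primary statistician also stays blinded to cohort labels until the analysis is finished (section 2.5), so the choice could not easily be steered towards the app. This stands and limits the harm, but the outcome of the check is still not fixed.

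**The size is small where it would count.** In the 3% v 5%, 5% v 8% and 8% v 10% examples, both standard errors give z between 3.8 and 6.8, so no conclusion changes, even after the Bonferroni correction for nine tests. For unadjusted differences near z = 2 the shift is only about 1% to 2%: 8% v 9.05% gives 0.991, and 2% v 2.5% (z about 1.85) gives 0.983. This stands for unadjusted comparisons. Covariate imbalance can still produce a few percent with no effect at all, as in step 3.

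**Stronger readings that the document does not support.** A reader might infer that unequal variance is certain for the count and proportion outcomes too. It is usual there, but not a mathematical necessity. A reader might also count fitted risks below 0 as a harm, or conclude that logistic regression is required. The target is an average treatment effect reported as an adjusted mean difference, which for a 0/1 outcome is a risk difference. No individual risk is predicted, and the linear probability model is a legitimate way to estimate it. Linear against logistic is a matter of preference.

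**Conclusion.** The point holds as a minor weakness of prespecification. For the six clearly yes/no secondary outcomes, and for weight gain if coded that way, the validity of constant-variance standard errors is a question that should not be left to a plot. The error is 0 to about 5% of the standard error in either direction, with nominal 95% coverage of about 94% to 96%. Its direction depends on which cohort is larger and on how covariates relate to downloading.

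These sizes rest on assumed event rates, baseline prevalence and download rates. It would go too far to infer that the secondary p-values are unreliable or that type I error is inflated in general: with equal rates and no covariate imbalance the ratio is exactly 1.

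**What to change.** Replace the residual-plot trigger in section 3.1.1 with a statement that heteroskedasticity-robust (sandwich) standard errors will be used for all outcome models. Add to section 3.1.2 that the yes/no outcomes are analysed as adjusted risk differences from the linear model with those errors. Residual plots can stay as a description of model fit.

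The cost is a line or two of SAP text and one option in the R code. The downside of robust errors is negligible at n = 12,344. The choice of confounders, the effect measure and the multiplicity rule are unaffected.

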A Blinded Evaluation of the Effectiveness and Efficacy of the MyHealthyPregnancy Application Statistical Analysis Plan

This study will evaluate the effectiveness and efficacy of the MyHealthyPregnancy App, an app designed to reduce preterm birth risk. This study will use observational cohort data collected at the University of Pittsburgh Medical Center between September of 2019 and February of 2022.

July 18, 2022

[name], [name]

1. Description of the study

MyHealthyPregnancy (MHP) was developed using decision science principles to help prevent preterm birth. An observational cohort trial was conducted at the University of Pittsburgh Medical Center starting in September of 2019 until February 2022. This trial compares the effectiveness of MHP to usual care for pregnant people who delivered at the University of Pittsburgh Medical Center (UPMC). Patients at UPMC were able to download the MHP app after receiving a prescription for the app, as indicated by an EHR variable. Those who were prescribed the app and downloaded it were in the *MHP cohort*. Those who were prescribed the app and did not download it were in the *usual care cohort*. Prescriptions were offered to pregnant people by their care team at an early prenatal visit at UPMC.

EHR data is available for both cohorts of patients. It is the source of all measures, unless otherwise noted.

A linear effects model will be used to evaluate effectiveness by estimating the average treatment effect for the primary endpoint, preventing preterm birth risk.

For each dependent measure, these models will control for primary predictors, as identified in the research literature, that are available in the EHR.

A dose-response model will be used to estimate the effects of continuous measures of non-adherence (as opposed to dichotomous non-adherence, such as not initiating app use). Multiple measures of adherence will be analyzed, including measures of daily use, weekly use, time to initiation, and time from discontinuation to birth.

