1.1.2. Secondary objectives

1. To compare *preterm birth*, defined as delivery before 37 gestational weeks, for the MHP and usual care cohorts. Analyses control for predictors of preterm birth.
2. To compare *depression* rates for the MHP and usual care cohorts, using the clinical diagnosis of depression. Analyses control for predictors of depression.
3. To compare *anxiety* rates across MHP and usual care cohorts, using ICD10 codes. Analyses control for predictors of anxiety.
4. To compare rates of *referrals to behavioral health specialists* for the MHP and usual care cohorts. Analyses control for predictors of behavioral health referrals.
5. To compare rates of *referrals to social workers* for the MHP and usual care cohorts. Analyses control for predictors of social work referrals.
6. To compare rates of *preeclampsia* for the MHP and usual care cohorts. Analyses control for predictors of preeclampsia.
7. To compare *sufficient gestational weight gain*¹ for the MHP and usual care cohorts. Analyses control for predictors of gestational weight gain.
8. To compare the number of *prenatal appointments attended* for the MHP and usual care cohorts. Analyses control for predictors of prenatal appointment attendance.
9. To compare the proportion of *required prenatal appointments attended* in the MHP and usual care cohorts. Analyses control for predictors of prenatal appointment attendance.

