3.1.5. Additional statistical considerations

Method for handling confounding by indication

Because this trial is observational, there may be incomplete overlap in covariates between the MHP and usual care cohorts. To account for this possibility, inverse probability of treatment weighting will be used. Propensity score matching of comparable subgroups will also be used and reported as a sensitivity analysis (13).

Propensity score matching works by creating samples of participants who have the same likelihood of receiving treatment. Logistic regression will be used to generate propensity scores; nearest-neighbor matching without replacement will be used for matching. Baseline confounders will be included in the propensity score model, if they are related to the likelihood of receiving treatment and the outcome. Date of first visit will not be included in the model (for reasons given in Section 3.1.1). Participants without similar propensity scores, defined as greater than a caliper width, will be excluded from this sensitivity analysis. The average treatment effect will be calculated for the included subset of similar participants.

Austin recommends a “caliper width,” defined as the difference between two propensity scores, as “equal to 0.2 of the standard deviation of the logit of the propensity score”(14). To balance the internal and external validity of this sensitivity analysis, this caliper width will be used, unless it excludes more than 20% of the sample. In that case, the caliper width will be increased until 80% of the participants are included. If this is adjustment is needed, the results using the smaller caliper width will be reported in the supplemental material. Following Austin (2011), standardized differences, QQ-plots, box plots, cumulative distribution functions, and empirical nonparametric density plots will be used to check the differences in baseline covariates between the treated and untreated samples (13).

Time-effects

For the primary models, we have chosen not to include the first appointment date as it could capture factors that affect the effectiveness of the app. During the study time frame, many outside factors could have affected the outcomes, especially due to the COVID-19 pandemic.

Because of this we will conduct a sensitivity analysis including a time effect, the date of the participant's first prenatal visit, in each model.

4. Software

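### The objectives promise control for predictors of secondary outcomes 4, 5, 8 and 9, but section 3.1.2 names none, so their literature-only model adjusts self-selected cohorts for hospital alone

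*SAP*

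**What the plan says.** Three places in the SAP promise covariate control:

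- Section 1 says of each dependent measure that "these models will control for primary predictors, as identified in the research literature". The sentence then limits this to predictors held in the EHR.
- Section 1.1.2 makes the promise item by item and without that limit. For outcome 4 it reads "Analyses control for predictors of behavioral health referrals". Outcomes 5, 8 and 9 carry matching sentences.
- Section 3.1.2 says "Each outcome will have its own appropriate confounders", taken from earlier research and fixed in advance.

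The list in 3.1.2 then gives "No confounders identified" for outcomes 4, 5, 8 and 9.

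On modelling, 3.1.1 says "We will report the results of two models for each outcome, one using only confounders identified in the literature" and one that adds covariates chosen empirically. It also says "We will include hospital location as a variable in all models". Section 3.1.5 adds that "inverse probability of treatment weighting will be used", with propensity score matching as a sensitivity analysis.

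For outcomes 2 and 3, 3.1.2 lists prior anxiety and depression as a literature confounder. Appendix A defines the any-time depression outcome so that it "would also be 1 if PREGSTART_DEPRESSION is 1", and the anxiety outcome is coded in the same way.

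**The concern.** By 1.3, the cohorts are formed by each person's own decision to download. A model with cohort and hospital only can therefore show a difference that reflects who downloads and not what the app does. For four of the nine secondary outcomes, one of the two reported models has this form, while the objectives tell the reader that predictors are controlled.

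Section 3.1.1 explains the two models as a trade-off between representativeness and bias. It does not say which one supports the conclusion when they disagree.

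For behavioral health referral the gap is avoidable from the SAP's own content. Prior anxiety and depression are already accepted as confounders of those diagnoses, and both first-visit flags are in Appendix A, yet the referral outcome receives neither.

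**Working it through.** **Text check.** For outcomes 4, 5, 8 and 9 the literature list is empty and hospital is in every model. The literature-only model is therefore cohort plus hospital. In the second model, every covariate beyond hospital must come from the 20% subset.

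**Inputs from the SAP.** Cohorts of 7147 and 5197 (1.5); 5% level with Bonferroni over 9 secondary outcomes (3.1), taken as two-sided; a 20% subset split evenly between cohorts (2.5); a 10% change-in-estimate rule (3.1.2). The SAP gives no figure for these four outcomes. Its power statement for the primary outcome reproduces with the same cohort sizes: (1.960 + 0.842) × √(1/7147 + 1/5197) = 0.0511 SD, or 0.51 day at an SD of 10 days.

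**Assumptions.** There is no app effect. Baseline anxiety or depression is 20% in one cohort and 20% + d in the other. Referral is 20% with and 5% without that illness. The imbalance d remains within hospitals, so the hospital term is left out of the calculation.

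**Outcome 4, literature-only model**

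- Expected referral: 0.05 + 0.20 × 0.15 = 0.080 in one cohort and 0.05 + (0.20 + d) × 0.15 in the other.
- False difference: d × (0.20 − 0.05).
- SE = √(pA(1 − pA)/7147 + pB(1 − pB)/5197), and z = false difference / SE.
- Chance of significance: Φ(z − c) + Φ(−z − c), with c = 1.960 uncorrected and c = 2.773 at 0.05/9.

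| d | False difference | SE | z | p < 0.05 | After Bonferroni |
|---|---|---|---|---|---|
| 2 points | 0.30 points | 0.00498 | 0.60 | 9% | 1.5% |
| 5 points | 0.75 points | 0.00503 | 1.49 | 32% | 10% |
| 10 points | 1.50 points | 0.00512 | 2.93 | 83% | 56% |

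Swapping the cohort sizes changes these percentages by at most about one point. Uncorrected range over the same d: 6%, 9%, 21% if referral is 10% v 5%; 15%, 61%, 99% if it is 30% v 5%.

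**Outcome 4, second model.** A simulation of 4,000 runs applied the 10% rule to 1,234 per cohort (12,344 × 0.20 / 2 ≈ 1,234), then fitted a linear model with robust standard errors to all 12,344. Baseline illness was selected in 86%, 99.6% and 100% of subsets at d = 2, 5 and 10 points. The share with p < 0.05 was 9%, 30% and 84% in the literature-only model, and 6%, 5% and 6% in the second model.

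**Outcome 8, literature-only model.** Assume an SD of 4 visits and a gap of 1 visit between levels of an omitted covariate. SE = 4 × √(1/7147 + 1/5197) = 0.073. False differences of 0.02, 0.05 and 0.10 visits give z = 0.27, 0.69 and 1.37: about 6%, 10% and 28% uncorrected; 0.7%, 2% and 8% corrected. A gap of 2 visits gives 9%, 28%, 78% and 1.4%, 8%, 49%. Outcomes 5 and 9 were not calculated.

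**Outcomes 2 and 3.** If prior history enters as the outcome's own first-visit flag, people positive at that visit always score 1 and add nothing to the cohort contrast. With assumed new-diagnosis risks of 8% v 6% and equal baseline prevalence of 10%, 20% or 30%, the adjusted any-time difference is (1 − prevalence) × 2.0 = 1.8, 1.6 or 1.4 points, with z = 4.13, 3.89 and 3.64. Restricting to first-visit negatives gives 2.0 points and the same z each time.

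Without the flag, assume baseline prevalence of 25% v 20% and new-diagnosis risk of 7% in both cohorts. The difference is then (0.25 + 0.75 × 0.07) − (0.20 + 0.80 × 0.07) = 0.3025 − 0.2560 = 4.65 points (z = 5.7) with no app effect.

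**The case against.** The strongest reply on outcomes 4, 5, 8 and 9 is that the plan does control for confounding. Hospital is in every model, a second model adds empirically chosen covariates, and weighting and matching follow. The promise in section 1 covers only predictors found in the literature and held in the EHR, so an empty list openly reports that the search found nothing. Readers will see the thin model beside a fuller one. Every rate above is assumed, and the largest figure needs a 10-point imbalance, a fourfold referral ratio and no multiplicity correction.

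Much of this stands. The wording of section 1 is qualified, and the second model returns to about 5 to 6% false positives in the simulation. It does not remove the conflict between 1.1.2, which has no qualifier, and 3.1.2. Nor does it say which model decides, or explain why the referral model lacks history flags that the SAP accepts elsewhere. Whether the literature offers predictors of social work referral or attendance cannot be judged from the SAP.

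A reader might also infer from the any-time coding that the depression and anxiety comparisons are invalid, or that new diagnoses go untested. The SAP does not support that. History is already a listed confounder for both outcomes, and if it is entered as the outcome's own first-visit flag, the planned test is in effect the test of new diagnoses. Section 1.1.2 sets out to compare rates and does not promise new cases. The smaller estimate follows from that choice of measure.

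**Conclusion.** The inconsistency on outcomes 4, 5, 8 and 9 is real and worth correcting before analysis. The harm is confined to the literature-only model. It would be wrong to infer that these outcomes have no adequate adjustment anywhere in the plan.

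The size depends on rates the SAP does not give. For behavioral health referral under the central assumptions, the false difference is 0.3 to 1.5 points for imbalances of 2 to 10 points. At a 2-point imbalance the distortion is small; at 10 points it would usually reach nominal significance. These figures also assume that the imbalance remains within hospitals.

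For outcomes 2 and 3, only a clarification is needed. The SAP does not say which variables represent prior anxiety and depression, and leaving the outcome's own flag out would pass any baseline imbalance into the result.

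**What to change.** 1. Before the 20% subset is viewed, add PREGSTART_DEPRESSION and PREGSTART_ANXIETY to 3.1.2 as a priori covariates for behavioral health referral.
2. At the same time, name baseline covariates from Appendix A for outcomes 5, 8 and 9, with a reason for each. Insurance and area deprivation are candidates that the authors would have to justify.
3. Where none can be justified, state that the empirically adjusted model supports the conclusion for that outcome, and correct the promise in 1.1.2.
4. For outcomes 2 and 3, state that prior history is entered as the PREGSTART_DEPRESSION and PREGSTART_ANXIETY flags. A separate analysis of new diagnoses among first-visit negatives is optional and not a correction.

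The cost is SAP wording and a few extra terms in models already planned. All the variables are held, and no new data or added analysis is required.
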